Overall, CBD administered in various forms demonstrated a favorable safety profile in these controlled clinical trials. There is also preliminary evidence that CBD may be a useful treatment for several other medical conditions. Several current studies located on clinicaltrials.gov will begin or have begun recruiting subjects and collecting data in efficacy studies investigating CBD ingestion and its therapeutic effects for reducing chronic and musculoskeletal pain and anxiety-related disorders (social anxiety disorders).

Experimental Injury Model

The experimental injury model we will employ for this study is a controlled model of muscle micro-trauma and recovery. This particular experimental model was selected because it allows us to control and standardize the mechanism of injury and allows us to track symptomatic response and physical impairment in a more clinically relevant manner when compared with other experimental pain models that are controllable but of shorter duration (e.g. thermal or pressure stimuli). The experimental model requires the participant to complete a single bout of high intensity resistance exercise. The exercise bout is able to systematically optimize eccentric overload of the muscle coupled with fatigue to produce controlled strain-induced damage to the contractile elements of the muscle. The resultant muscle injury produces a local inflammatory response with associated soreness, stiffness, disability, and functional deficits.²⁸⁻³¹ Our previous findings from work in the shoulder, arm and low back generate pain and disability in subjects. We have also demonstrated an established link between this pre-clinical pain model and a post-operative clinical pain model suggesting robust validity.^{32,33} Last, these models form the basis for trials funded by the NIH to study other interventions for pain.

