Inclusion Criteria: a) male and female adults between the ages of 18-35 years and b) English speaking, and c) both female and male subjects must be currently practicing acceptable methods of birth control, such as abstinence, and methods of contraception (barriers, oral, patch or other prophylactic methods).

Exclusion Criteria: (a) use of cannabis products on a regular basis OR positive urine test for cannabis, (b) history of seizure disorder (self or family), traumatic brain injury, liver, kidney, or cardiovascular disease, (c) current medical condition that would prevent the participant from performing strenuous resistance exercise, (d) weight lifting for the lower extremities (legs) more than twice a week, (e) currently experiencing pain in the hips, leg, or knee region, (f) pregnancy, lactating or positive urine pregnancy test, (g) known allergy to CBD, coconut/sesame oil, or tree nuts (coconut).

If the participant self-reports that they are currently using tobacco products or a nutritional/dietary supplement, or if they take prescription anti-depressant/anxiety medications, the participant may continue to use the product(s) but they must be on a stable dose at least 3 months prior to randomization as well as during the 15-day study trial period. Also, if the participant is currently using OTC anti-inflammatory medication (e.g., Advil, Aleve, Aspirin) on a regular basis, we will ask that they stop taking the medication at least 7 days before randomization and refrain from using the product during their participation in the study trial.

Investigational Product & Dosing Schedule

Participants will be provided a 30mL bottle with a syringe dropper on day 1 with instructions to ingest the solution orally using a sublingual route of administration (0.5 cc ~1/2 dropper) twice per day (BID) 12 hours apart (morning and evening) at the prescribed daily dosages: Vehicle-control (0mg/30mL hemp extract = no hemp extract), and active Dose (2000mg/30mL hemp extract = 67mg/day). The sublingual route of administration allows the product to be absorbed directly into venous circulation, and thus bypasses the liver and eliminates the consequences of first pass metabolism; ultimately increasing its bio-availability. The bioavailability of CBD administered orally (including sublingual) is estimated to be 13-19% and its half-life estimated to be around 18-32 hours. 35,36

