Results of urine screening for pregnancy and toxicology (presence of cannabinoids) will be available and assessed during the first visit. If the urine test (pregnancy or cannabinoids) comes back positive, the participant will be excluded from the study. The participant will complete several psychological questionnaires (FPQ-9, PCS, PASS-20, PSQI, & LEFS), followed by tests for muscle soreness and quantitative sensory testing (QST). Each participant will be provided a detailed safety monitoring checklist of side effects and/or adverse reactions that they may potentially experience from ingesting the investigational product. Participants will then be instructed on how to perform their own passive surveillance for identifying these side effects/adverse events and what to do if they experience any of them between study visits while they are ingesting the investigational test article (Days 1 through 10). Participants will be instructed to maintain current activity levels and not to initiate a resistance-training or weightloss program for the duration of the study. Participants will then be randomly assigned to an experimental group and instructed on how to ingest the investigational test article (or placebo) and dosing procedures, which will be dispensed in a quantity to last for the next 15 days. Each participant will be provided a daily log chart to record their daily CBD doses for compliance and monitoring purposes. A pre-exercise visit will be scheduled. Each subject will receive \$10 for completion of the test session.

During the passive surveillance period (Days 1 through 10) participants will be instructed to contact the PI ([name]) if they experience any of the side effects/adverse events from the checklist provided at the baseline visit. [name]/[name] will then contact the study physician ([name]) for consultation. The side effects/adverse reactions will be triaged as mild, moderate or severe, and a determination will be made as to whether the side effect/adverse reaction is due to the investigational product or some other circumstance (e.g. food poisoning). If the event is determined to be due to the investigational test article and graded moderate to severe by the study physician, the participant will then be instructed to stop participation and seek medical care by their primary physician or hospital. Any participant that reports a serious adverse event will be followed to full resolution.

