Visit 2 (Pre-exercise measurements and exercise protocol, Day 11)

Participants will be assessed actively (including vital signs) at each subsequent visit by study personnel using the side effects/adverse events checklist. Each participant will be read each side effect/adverse reaction from the checklist and instructed to self-report as yes (go) or no (no go). For participants who continue in the study, the following procedures will be performed: completion of psychological questionnaires (FPQ-9, PCS, PASS-20, PSQI, & LEFS), followed by tests of muscle soreness, quantitative sensory testing (QST), the timed stair climbing test (TSCT) and isometric strength measures to evaluate leg function. Participants will then undergo a standardized single bout of eccentric resistance exercise to the dominant quadriceps muscle. An isokinetic dynamometer (Biodex System 4 Pro, Biodex Medical Systems, Inc., Shirley, NY) will be used for the eccentric exercise protocol. Each participant will then perform five sets of twenty-five repetitions. Exercise will be performed using concentric (meaning shortening of muscles during contraction) and eccentric (lengthening of the muscle while still developing tension). The angular velocity will be set at 60°/sec for concentric and 90°/sec for eccentric actions. Participants will be given a three-minute rest period between sets. Each subject will receive \$15 for completing the test session.

Visit 3, 4, & 5 (Follow-up measurements @ 24, 48, & 72-hr post-exercise, Day 12, 13, & 14)
The following procedures will be performed: completion of psychological questionnaires (PCS & LEFS), followed by tests of muscle soreness and leg function testing (TSCT and isometric strength measures). Participants will receive \$5 for completing visits 3, 4 and 5.

Visit 6 (Follow-up measurements @ 96-hr post-exercise, Day 15)

The following procedures will be performed: completion of psychological questionnaires (FPQ-9, PCS, PASS-20, PSQI, & LEFS), followed by tests of muscle soreness, QST, and leg function testing (TSCT and isometric strength measures). At the end of the session each participant will be asked if they thought they were taking the active CBD product or placebo. Participants will receive \$10 for completing visit 6.

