Study personnel will perform a follow-up phone call at 1 week after completion from the study for continued safety monitoring. Study personnel will refer to the checklist to determine if the participant has experienced or is experiencing any side effects or adverse events using the safety monitoring guidelines. If the participant reports experiencing any of the side effects/adverse events from the checklist the study physician will be consulted immediately for guidance and the participant's condition will be followed until full resolution.

Primary Outcome Measures: Self-report ratings of muscle soreness will be used to determine efficacy for duration of soreness and peak intensity of soreness. A muscle soreness inventory will be used to self-report the level of soreness. The muscle soreness inventory consists of rating soreness on a visual analog scale (VAS). A 10cm line is drawn with 0 (no soreness) on the left pole and 10 (extreme soreness) on the right pole. The inventory asks participants to rate their level of soreness by placing a slash on the line that best represents

their current level of soreness and soreness at its worst, best and average over the past 24 hours. The highest worst soreness intensity recorded during the recovery time will be recorded as the peak intensity of soreness. Measures of anxiety and fear of pain/soreness will also be recorded using a similar VAS. **Disability** will be measured using the Lower Extremity Functional Scale (LEFS).³⁷ The LEFS is a self-report questionnaire containing 20 items concerning an individual's ability to perform everyday tasks. The scale can be used to evaluate the functional impairment of a patient post-exercise of one or both lower extremities. Each item includes a 0-4 point hierarchical grading scale with 0 being "extreme difficulty or unable to perform activity" and 4 being "No difficulty". Subjects will rate their level of function for each of the 20 items for a total of 80 points. Each subject's score will be divided by 80 and recorded as a percentage value. LEFS scores will be recorded regularly until recovery and the highest score during this period will be recorded as peak lower extremity disability.

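### Leg training is allowed up to and through the recovery window but not recorded, so participants' own workouts can add to the soreness and disability outcomes

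*Combined protocol and SAP*

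**What the plan says.** Exclusion (d) under Study Population removes people doing "weight lifting for the lower extremities (legs) more than twice a week". Those who train legs once or twice a week are eligible, and no limit is set on running, cycling or sport.

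The Visit 1 section gives the only activity rule: "Participants will be instructed to maintain current activity levels and not to initiate a resistance-training or weightloss program". The sentence goes on to apply this to the whole study. The bar on starting a programme does not reach someone who already has one.

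The injury is induced on Day 11: "Participants will then undergo a standardized single bout of eccentric resistance exercise to the dominant quadriceps muscle". Follow-up then runs through "Follow-up measurements @ 24, 48, & 72-hr post-exercise, Day 12, 13, & 14" and "Follow-up measurements @ 96-hr post-exercise, Day 15".

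Under Primary Outcome Measures, participants rate "their current level of soreness and soreness at its worst, best and average over the past 24 hours". Peak soreness is the highest of the worst ratings over recovery, and duration of soreness is also an efficacy measure. LEFS, the disability measure, may reflect one or both lower limbs.

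The daily log described at Visit 1 is for doses, and the visit checklist is for side effects. The repeated-measures ANOVA under Data Management & Analysis names no term for training.

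**The concern.** The outcomes are meant to describe the response to one supervised bout on one muscle. The Experimental Injury Model section chose this model partly because "it allows us to control and standardize the mechanism of injury". Yet a participant who follows the activity rule may load the same muscle on their own shortly before Day 11 or during the four follow-up days.

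- **Before Day 11.** A session may shift the Visit 2 pre-exercise values for soreness, LEFS, isometric strength and stair time, which are the reference for recovery.
- **During Days 12-15.** A session may raise the worst-soreness rating, prolong the measured duration of soreness, or affect LEFS through either leg.

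The ratings carry no attribution, so the data cannot separate this soreness from that of the induced injury. The plan does restrict another influence on soreness: regular users of over-the-counter anti-inflammatories must stop 7 days before randomisation and avoid them during the trial. Leg training has no matching rule.

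**Working it through.** The protocol states no power, effect size or SD, so it has no figure of its own to reproduce. The check is therefore on timing, followed by an illustration of the cost in precision.

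**Inputs from the protocol.** Permitted frequency: 0, 1 or 2 leg sessions a week (exclusion (d)). Activity rule: "maintain current activity levels and not to initiate a resistance-training or weightloss program for the duration of the study". Bout on Day 11; follow-up on Days 12, 13, 14 and 15, a window of 4 days. Allocation 15 and 15. Significance level 0.05, taken as two-sided because sidedness is not stated.

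**1. Chance of an own session in the window.** Put s sessions on random distinct days of a 7-day week, none skipped. For a window of w days, P(at least one) = 1 − C(7−w, s)/C(7, s), and the expected number is w × s/7.

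| Window | 1 session/week | 2 sessions/week |
|---|---|---|
| Days 12-15 (w = 4) | 1 − 3/7 = 57%; expected 0.57 | 1 − 3/21 = 86%; expected 1.14 |
| Days 11-15 (w = 5) | 1 − 2/7 = 71%; expected 0.71 | 1 − 1/21 = 95%; expected 1.43 |

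If two weekly sessions are never on consecutive days, 14 day-pairs are possible and 1 misses Days 12-15, so P = 1 − 1/14 = 93%. The five days before the bout (Days 6-10) are also a 5-day window, so the chance of a session there is again 71% or 95%.

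**2. Cost in precision (assumed inputs).** For a simple two-group comparison, the detectable standardised difference at 80% power is (1.960 + 0.842) × √(2/15) = 1.02 SD (1.06 SD with the t distribution).

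Assume that a fraction f = 20-60% of participants lift, that q = 4/7 to 6/7 of these have a session in the window, and that a session adds a = 0.5-1.5 SD to peak soreness, equally in both arms. None of these values of f and a is in the documents. With p = f × q, the SD is multiplied by √(1 + a²p(1−p)).

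- Low end: f = 0.2, q = 4/7, a = 0.5. Then p = 0.114 and the SD factor is √(1 + 0.25 × 0.101) = 1.01. Power is 79%, and 16 per arm restores 80%.
- High end: f = 0.6, q = 6/7, a = 1.5. Then p = 0.514 and the SD factor is √(1 + 2.25 × 0.250) = 1.25. Power is 61%, and 24 per arm restores 80%.

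**3. Chance imbalance.** With the number of lifters in each arm binomial (15, f) and no stratification, the arms differ by three or more lifters with probability 25% at f = 20% and 35% at f = 40% or 60%.

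**The case against.** **Own workouts during recovery are not established.** A reader might infer that they do fall in the window and are scored as the induced injury. The documents do not support that. They give no share of lifters and no training days, people who do not lift are also eligible, and a sore participant may skip a session. An expected count of 1.14 is not a guarantee of one session, and it applies only at the highest permitted frequency. This objection stands, and the percentages are upper figures in so far as soreness cancels sessions.

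**Added soreness is not shown.** Nothing in the protocol says that an accustomed session adds to soreness from five sets of 25 repetitions designed for eccentric overload, or that it would set the peak. This also stands. The point is that such sessions can contribute and that nobody could tell.

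**The injury remains standardised.** A reader might infer that the model's rationale collapses. It does not: the claim concerns the mechanism, which is the supervised dynamometer bout, and that is the same for everyone. What is uncontrolled is other loading around it.

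**Randomisation and baseline measurement help.** Randomised, blinded allocation makes training habit non-differential on average, so the main effect is noise, and the low-end illustration costs only one percentage point of power. Visit 2 measures are taken before the bout, so raised pre-exercise values could be seen. They could not be attributed to training, and Visit 2 tells nothing about Days 12-15.

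**Some material is not visible.** The phone screen is cited but not shown, and consent pages were removed. Either could carry an activity instruction. The finding is limited to the text available.

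**Conclusion.** The concern holds as a gap in control and recording. By the plan's own rules, people who train legs once or twice a week may enrol and are told to carry on, and no available text suspends or records that training around the bout. For such a participant the chance of at least one own session in Days 12-15 is about 57% at one a week and 86% at two, if days are random and none is skipped.

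The likely consequence is extra variability in a study that can detect only about 1 SD with 15 per arm. Under the assumed ranges the SD rises by 1-25% and power falls from 80% to between 79% and 61%. Those figures show scale and are not estimates.

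A reader might go further and infer a biased comparison between arms. The documents do not show that. Bias could arise by chance imbalance, or if the product changes when people return to training, for instance if less soreness leads to earlier training and new soreness. The plan collects nothing with which to examine either. The change is worth making because it is cheap and the study is meant to inform a larger trial.

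**What to change.** 1. **Instruction at Visit 1.** Ask participants to keep to their usual activity, except for no leg resistance training and no unaccustomed strenuous leg exercise from Day 6 until the Visit 6 measurements are complete. Day 6 is 5 days before Visit 2. It borrows the 4-5 days within which the risk section on the exercise protocol expects symptoms to be much reduced.
2. **One yes/no question at Visits 2-6.** Ask about leg exercise since the last visit (at Visit 2, since Day 6).
3. **Sensitivity analysis.** Keep all participants in the main analysis, report the answers by arm, and repeat the analysis excluding or flagging those who trained. Training after randomisation may itself depend on treatment, so this analysis is supportive only.
4. **Keep Visit 2 on Day 11 whatever the answer.** Rescheduling would make the 10-day wash-in differ between participants and run past the 15-day product supply.

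The cost is one changed instruction, one question at visits that already take place, and one extra analysis. Days 6-15 are 10 days, so a twice-weekly trainee forgoes 10 × 2/7 = 2.9 sessions, that is two or three. No added staff or procedures are needed.

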We will be able to study important bio-behavioral factors in a concomitant manner that are specific to the central tenets of ingesting a hemp-extract that contains CBD and other minor cannabinoids. Biological factors to be studied include clinical signs of reduced symptomatology and functional limitations as well as quicker recovery to baseline that are indicative of anti-inflammatory and analgesic effects of CBD ingestion. Additional prior work by our group shows robust associations among pain intensity and measures of negative affect. Thus, we will also be able to study pain-related fear-avoidant and anxiety behaviors that are involved in the participants' perception of the threat or anticipation of a painful experience related to intense exercise and injury before, during and after undergoing our experimental injury model.

5. Specific Aims of Study:

Our overall objective is to generate preliminary data in humans on the effects of ingesting a hemp-extract investigational product that contains CBD for reducing pain-related anxiety and symptoms related to induced muscle injury. We aim to determine the efficacy of a controlled short-term trial of hemp-derived CBD ingestion for reducing symptomatic response and facilitating recovery following induced muscle injury. We will assess, in serial fashion, symptomatic response (both physical and psychological factors), functional limitations and recovery of the quadriceps muscle following induced injury in which selected doses of a hemp-derived CBD oil will be administered orally during a 15-day pre-injury consumption and post-injury recovery phase. We will evaluate these responses with an experimental repeated-measure design spanning pre-treatment, baseline measurement, injury induction, short-term sublingual administration of a hemp-derived CBD extract (or placebo) and recovery.

Aim 1: To determine time-related patterns of symptomatic and functional recovery in response to sublingual administration of either a low-dose or a high-dose CBD extract after muscle injury. Based on the purported anti-inflammatory, analgesic, and anxiolytic effects of CBD ingestion, we hypothesize that short-term sublingual administration of a hemp-derived CBD extract will limit the symptomatic response and functional limitations after induced muscle injury allowing for an expedient recovery to baseline conditions.

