Aim 2: To determine the impact of sublingual administration of a CBD extract on psychological factors known to influence pain intensity and duration. The investigation of psychological constructs will include evaluating the effects of sublingual administration of a CBD extract on pain-related anxiety, catastrophizing and fear pertaining to participants' views and perceptions toward engaging in strenuous physical exercise, sustaining a musculoskeletal injury and prolonged symptomatic and functional recovery. We hypothesize that the anxiolytic effects of sublingual administration of a CBD extract will diminish the threat and perceived physical stress of exercise-induced pain, physical harm, and prolonged symptomatic and functional recovery.

This exploratory study will provide preliminary data needed to support the hypotheses of a planned larger scale application. Preliminary data will help in better designing a future study aimed at identifying an efficacious dose range of hemp-derived CBD extract, as well as determining the cellular and molecular mechanisms that contribute to symptom resolution and recovery. Our findings may also be helpful for making future improvements for treating a broader range of inflammatory conditions that afflict the musculoskeletal system.

6. Research Plan:

Study Location & Design

The project will involve one study center located on the campus of the University of Florida. Data collection for the study will take place in the Sports Medicine & Human Performance Research Laboratory ([name]). The study protocol will be submitted to the UF Gainesville Health Science Center Institutional Review Board (IRB-01) located in the Gainesville Health Science Center ([name]).

The design will be a double-blind, randomized, vehicle-controlled, three-arm trial. Participants will be randomly assigned to either an active CBD dose group (n=15) or vehicle-control (placebo) group (n=15).. The effects of the active CBD dose groups will be compared to the vehicle-control. Subjects will be required to complete a 15-day study trial spanning a presupplement baseline visit, a controlled daily dosage regimen, pre-exercise baseline testing, eccentric exercise to induce muscle damage, and planned follow-up post-exercise data collection time points.

Study Population

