Exercise Protocol: Participants will likely experience some level of discomfort in their upper thigh (quadriceps muscle) following the exercise protocol. The discomfort will be in the form of localized muscle soreness, stiffness, and limited motion. These symptoms have been shown to last short-term and should be significantly diminished within 4-5 days. Based on our previous experience, the chance of this occurring is rare, occurring in less than 1% of the population (less than 1 out of 100). As with any type of resistance exercise there is a slight risk of repetitive strain injury. We have used this exercise protocol in our previous studies without any incidence of significant injury or any other related adverse reaction. All muscle resistance exercise sessions will be investigator supervised to minimize the probability of muscle injury. Furthermore, in the unlikely event that an injury may occur, a National Athletic Trainers' Association Board-certified athletic trainer (ATC) or licensed physical therapist (LPT) will be available to direct immediate treatment, if required. All study personnel are first aid and CPR trained and certified.

Mechanical Pressure: pressure is administered to the surface of the skin at an approximate rate of 30kPa/sec via a hand-held algometer fitted with a 10mm diameter rubber tip. Participants will be instructed to signal pain by pressing a button (kill switch) when the pressure sensation becomes unpleasant. The algometer will be immediately removed from the surface of the skin upon signal from the participant. The risk of bruising or other skin trauma as a result of this procedure is minimal. By design, participants stop the procedure at the onset of discomfort (unpleasantness) but will be informed that they also can elect to discontinue the procedure at any time. In a separate assessment, punctate pressure stimuli will be delivered to the surface of the skin using a nylon monofilament. The procedure involves 10 pressure applications at a rate of one application per second. The risk associated with this procedure is minimal. Some participants may experience mild skin irritation and/or redness at the immediate punctate site

that will resolve within 1-3 minutes following the procedure. Participants may stop the procedure at any time at their request.

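### Duration of soreness is a named primary outcome with no definition and no rule for participants still sore at 96 h, and the Friedman fallback does not compare the arms

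*Combined protocol and SAP*

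**What the plan says.** Under Primary Outcome Measures (section 6, Research Plan) the protocol states: "Self-report ratings of muscle soreness will be used to determine efficacy for duration of soreness and peak intensity of soreness". The soreness inventory has four VAS items. Participants mark "their current level of soreness and soreness at its worst, best and average over the past 24 hours". Peak has a rule: "The highest worst soreness intensity recorded during the recovery time will be recorded as the peak intensity of soreness". No such rule follows for duration.

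Soreness is tested at Visit 1 (Day 1), at Visit 2 before exercise (Day 11), and at 24, 48, 72 and 96 h after exercise (Visits 3 to 6). The phone call one week later is for safety only. On the expected course, the Exercise Protocol risk text says: "These symptoms have been shown to last short-term and should be significantly diminished within 4-5 days". Aim 1 hypothesises that CBD limits symptoms, "allowing for an expedient recovery to baseline conditions".

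Study Location & Design sets the contrast: "The effects of the active CBD dose groups will be compared to the vehicle-control". Data Management & Analysis assigns the outcome measures to a two-way repeated-measures ANOVA (group between, time within) or a distribution-free test, with Friedman as the example. Tukey comparisons follow a significant interaction, significance is set at 0.05, and effect sizes with precision are promised for every outcome.

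**The concern.** Duration is half of the soreness efficacy statement and the most direct measure of Aim 1's faster recovery. As written, two analysts with the same data could derive different durations. They could choose different VAS items, different levels for resolved, different starting points, and different treatments of a participant who is still sore at 96 h.

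The last of these also bears on the comparison itself. If CBD shortens soreness, more vehicle than CBD participants will be unresolved at 96 h. Dropping them, or averaging them in as 96 h, removes or shrinks the difference the study is looking for. The promised effect size and precision for duration cannot be computed until these choices are made, and choices made after seeing the data can steer the result. The study is exploratory, but the protocol says of its output: "Preliminary data will help in better designing a future study". A shrunken difference would carry through to that study's sample size.

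The distribution-free fallback is a separate gap. If the data are judged unsuitable for ANOVA, Friedman as named would leave the between-arm question unanswered.

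**Working it through.** The plan gives no power, effect size, SD or expected duration, so there is no figure of its own to reproduce.

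**Text check.**
- VAS item: four are collected. Peak is assigned the worst rating; duration is assigned none.
- Threshold: the nearest text is the return to baseline in Aim 1's hypothesis. It names no item or tolerance, and does not say whether baseline means Visit 1 or Visit 2.
- Clock start: not stated.
- End of observation: 96 h, which is day 4. The risk text expects symptoms to be diminished, not gone, by days 4 to 5. Unresolved soreness at the last rating is therefore plausible, though the documents give no rate.
- Tests: the ANOVA needs several values per participant. With a single derived value there is no time factor and no interaction for Tukey to follow; only the two-group comparison remains. Friedman ranks within participants and has no group term. On one value per participant it cannot be run at all.

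**Illustration of the 96 h rule.** From the protocol: 15 per arm, ratings every 24 h to 96 h, alpha 0.05 (taken as two-sided). Assumed, because the documents give nothing: log-normal durations, log-SD 0.4, CBD median 0.75 times the vehicle median, current-soreness item, complete follow-up.

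Share unresolved at 96 h = 1 − Φ[ln(96/median)/0.4]. For a vehicle median of 72 h: ln(96/72)/0.4 = 0.72, giving 24%. For CBD (54 h): ln(96/54)/0.4 = 1.44, giving 8%.

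True mean difference = 0.25 × vehicle median × exp(0.4²/2), and exp(0.08) = 1.083. For 120 h: 30 × 1.083 = 32.5 h.

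The observed differences and power come from simulation (40,000 trials per scenario), with each duration rounded up to the next visit:

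| Vehicle median (h) | 48 | 72 | 96 | 120 |
|---|---|---|---|---|
| Unresolved, vehicle vs CBD (%) | 4 vs 1 | 24 vs 8 | 50 vs 24 | 71 vs 44 |
| True mean difference (h) | 13 | 19.5 | 26 | 32.5 |
| Difference if coded 96 h (h) | 12 | 12 | 9 | 6 |
| Difference if dropped (h) | 11 | 10 | 7 | 5.5 |
| Power, coded 96 h, t-test (%) | 40 | 41 | 35 | 24 |
| Power, dropped, t-test (%) | 36 | 25 | 14 | 6 |
| Power, rank-sum, unresolved last (%) | 40 | 43 | 42 | 37 |
| Power, log-rank (%) | 40 | 42 | 41 | 37 |

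The power figures are good to about one percentage point.

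With no true effect, any one of the first three rules fixed in advance gives about 2.5 to 5.3% false positives, and log-rank about 5%. Keeping the smallest p of coded, dropped and ranked gives 6.7 / 8.6 / 10.5 / 9.3% across the four medians. Choosing only between coded and ranked gives about 5.3 / 6.8 / 7.8 / 6.8%.

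**The case against.** The strongest reply is that duration need not be one number per person. Aim 1 speaks of patterns over time, and Tukey comparisons after an interaction would show at which visits the arms differ. Read at group level, duration is how long each arm stays above its starting level. The ANOVA then fits and no individual needs a censoring rule. That reading is possible, so the text does not support saying that no named method can address duration. It is not written down either, and it still needs a VAS item and a level that counts as recovered.

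A reader might also infer that peak soreness has no valid test. That goes too far. Peak is defined, and with one value per participant the between-group term reduces to a valid two-group comparison. The abbreviation before Friedman marks it as an example and leaves room for another test. What stands is that the only distribution-free test named does not compare the arms, and no alternative is given.

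A reader might take 7 to 10% as the trial's false-positive rate. It is not. The inflation needs an analyst who tries several rules and keeps the best, and nothing in the documents indicates that intention.

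Finally, the large losses sit at assumed medians of 96 h or more. The risk text describes short-lived symptoms, and under a generous tolerance a diminished rating could count as resolved. At 48 to 72 h, coding unresolved participants as 96 h costs little or no power. All of this stands, as does the exploratory status of the study. None of it supplies the missing definition.

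**Conclusion.** The point holds as a gap in definition and method, not as evidence that the trial will fail. Duration of soreness is named as primary without an item, threshold, clock start or 96 h rule. The serial ANOVA is sound for the ratings themselves but neither produces a per-participant duration nor handles unresolved participants. Friedman does not answer the CBD-versus-vehicle question for any outcome.

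How much this matters depends on how long soreness lasts, which the documents do not say. Under the assumptions above, the choice between coding and a censored or ranked method is close to neutral at vehicle medians up to 72 h. At 120 h, coding leaves 24% power against 37% with log-rank, and shows a true 32.5 h difference as 6 h. Dropping is worse in every scenario. False-positive inflation arises only if the rule is picked after the data are seen. Even the best method reaches only about 40% power for a 25% reduction, so 15 per arm is the larger constraint. The plan should be changed because the remedy costs almost nothing.

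**What to change.** Before unblinding, add to Primary Outcome Measures and Data Management & Analysis:

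1. **Definition.** Duration is the time from exercise to the first visit at which one named VAS item is within a stated tolerance of its Visit 2 value, with no later scheduled visit above it. Recovery first seen at 96 h counts as an event.
2. **Comparison.** Use a log-rank or interval-censored method that treats unresolved participants as longer than 96 h and censors those who withdraw or miss visits earlier at their last rating. Rank-sum with unresolved participants ranked last is acceptable only if follow-up to 96 h is complete, because it cannot place someone lost at 48 h. Do not drop unresolved participants or average them as 96 h. Report the proportion recovered by each visit with 95% confidence intervals.
3. **Fallback and peak.** Replace Friedman with a between-arm distribution-free test. Compare peak soreness as one value per participant, by rank-sum or by ANCOVA on the pre-exercise rating, with a 95% confidence interval. Keep the repeated-measures ANOVA for the serial ratings.

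The cost is wording only: no new visits, data or participants. The tolerance has to be chosen and justified, and the result is less familiar than a mean duration. The choice of item is also a trade-off. Current soreness avoids the 24 h look-back but may read low at rest and differs from the item used for peak. The worst-in-24-h item matches peak but leaves more participants unresolved: under the same assumptions, 50% of vehicle and 24% of CBD participants at a 72 h vehicle median, against 24% and 8%.
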